- Any immunological disease requiring active therapy.
- Currently receiving Immunotherapy.
- Taking any prophylactic antibiotics at screening. Any prophylactic antibiotics must be stopped the day of the screening visit.
- Any known intolerance to the ingredients of the Uromune® Immunotherapy.
- Have any other condition or disease which, in the opinion of the investigator, could compromise participant safety or interfere with the participant's participation in the study or in the evaluation of the study results.

If a participant is found to have a UTI at screening, they are not excluded from the trial. Participants found to have a UTI at screening should be put on antibiotics. After completion of antibiotics and once negative urine test results have been received, participants may be eligible for screening deferral or rescreening as outlined below.

Participant Withdrawal

All participants may withdraw from the study at and point for any reason. They may withdraw at their own request or at the discretion of the investigator.

If a participant is withdrawn at any point between the Screening Visit and the Baseline Visit (Day 1) they will not be required to complete an Early Termination Visit as they will not yet have started study treatment. At any point after the participant begins taking study treatment (Baseline Visit), if they should withdraw for any reason, every effort should be made to complete the Early Termination Visit detailed below in the protocol. It should be documented in the CRF the reason for withdrawal and discontinuation of the study treatment. Any AEs or

SAEs should also be documented in the CRF at this end of study visit. Despite early discontinuation from the study, every effort should be made to follow AEs and SAEs as outlined in the Safety Reporting section of this protocol.

Screening Deferral and Re-Screening

At the time that a participant is screened, if they are found to have a current UTI, they are eligible for screen deferral or re-screening.

Deferral

A participant presenting with a UTI at the screening visit will be deferred from further participation in the study until after antibiotic treatment and receipt of negative urine results. These results must be received within the 4-week time period between the screening and the baseline visit in order for the participant to continue in the study. The participant will not be assigned a new study number.

Rescreen

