
Protocol Deviations

The study is to be conducted as described in the protocol without deviation unless there is a safety concern. The protocol must not be modified for any participant without the prior consent of the Research Ethics Board responsible at the investigative site.

Termination of the Study

If the Investigator discovers conditions during the course of the trial that indicate that the study should be discontinued an appropriate procedure for termination will be instituted.

Reasons for closure of the trial or termination of the study by the Investigator may include the following:

- Successful completion of the study at study site.
- Failure of Investigator to comply with the protocol, GCP guidelines or regulatory requirements
- Safety concerns

Rationale for Study Design

It would be difficult and really impossible to undertake a large multicenter randomized placebo controlled prophylaxis trial with limited funding. The need for evaluation of this type of intervention in Canadian female patients is unquestionable and the general efficacy and safety of Uromune® in Canadian women can be assessed using an open label real life observational study design employing using each participant's history of UTI as their own individual control. We will be able, within the number of participants planned for enrollment (convenience sample based on the number of individual Uromune® doses to be provided by supporting company) to answer our aim: To determine if Uromune therapy provides a clinically acceptable (efficacy and safety) prophylactic option in lieu of continuous and/or interval antibiotic dosing for Canadian women with a history of recurrent UTI.

We do not want to prove that this intervention is better than other interventions (in fact there are no other real non-antibiotic alternatives) but rather reduce the risk of recurrent UTI in women who are suffering from multiple UTIs requiring antibiotics. Each individual participant will be their own control based on the number of UTIs that are documented over the previous 12 months (to be included participants must meet the criteria of 3 documented UTIs requiring antibiotics over the last 12 months or 2 UTIs requiring antibiotics over the previous 6 months).

Number of Participants: Inmunotek, through its Canadian distributor, has offered the principle investigator at no cost, vaccine product (Uromune®) to treat up to 80 participants. The number of participants enrolled will be a convenience

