sample based on the early UK experience [2]. It is expected that 80 participants in total (with an expected drop out rate of 15%) enrolled at the Urology Centre at Queen's University site will allow a preliminary assessment of efficacy and safety. The UK early experience study reported that 78% (59 participants of a total of 75 evaluable participants) had no subsequent UTI in the 12 months after the vaccine was administered. One participant reported a treatment related rash while <10% of participants experience mild adverse reactions with only one participant temporarily suspending treatment. We anticipate that based on this experience, 80 participants will be sufficient to determine safety and potential efficacy.

Analysis

Primary outcome: The individual participant will be considered a complete responder if they have no UTI requiring antibiotics reported in the 12 months since initiating therapy. A 50% responder rate of all enrolled participants will be considered a very clinically significant result. Based on the results from the first experience report from the UK (Yang and Foley, 2017) with Uromune® which demonstrated that 78% of the 75 women who completed treatment had no subsequent UTIs in the follow-up period, our convenience sample should be sufficient to power our analysis. The primary efficacy endpoint will be considered to have been achieved if a clinically significant and important level of more than 50% of participants undergoing therapy has no reported UTI in the 12 months after initiation of therapy.

Secondary outcome: The number of UTI in individual participants requiring antibiotics in the 12 months after starting therapy will be compared to the number of UTIs requiring antibiotics before therapy is initiated (number over previous 12 months or 2 X the number over the preceding 6 months). The analysis will include individual participant data comparisons as well as the mean number of UTI before and after initiation of therapy in the entire cohort. Based on the results from the comparison of Uromune® vs antibiotics from Spain (Lorenzo-Gomez MF et al 2012) which demonstrated a mean UTI rate after Uromune® therapy (n=136) of 0.36 (CI0.29-0.44) at 6 months, 0.72 (CI 0.60-0.85) at 9 months, the study should be adequately powered to show a statistically significant difference in our convenience sample of participants enrolled with a history of at least 3 UTI in the preceding 12 months.

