Quality of life and satisfaction questionnaires will also constitute secondary endpoints

The analysis for both efficacy and safety will be an intent to treat analysis of all participants who took at least one dose of the Uromune®. A per protocol efficacy analysis will include all participants who completed the 3 month treatment regime.

Interim Analysis Plan and Stopping Rules

An interim analysis will be carried out when 50% of participants reach the 6month follow up interval. Stopping rules will be based on safety considerations – the study would be stopped if >20% (8 participants) experienced Treatment Emergent Serious Adverse Events (TESAEs). Safety will be monitored continuously for the rest of the study and the study will be stopped if at any time, if >20% of participants experience TESAEs.

Summary Statement: Rationale for this Investigator Initiated Early Experience Real Life Clinical Practice Study

We hope that this study will provide guidance for the use of Uromune® (when or if it is released in Canada) by providing information on the best way to manage recurrent UTI in individual participants using their own clinical data (in this case the number of recurrent UTI). The ultimate goal is to reduce participants' suffering (and therefore improve quality of life), participant time spent dealing with this problem, indirect costs (time off work or other activities), antibiotic use, antibiotic resistance and health care utilization (including costs). We plan to undertake this study with great enthusiasm with limited funding (and "in kind" supply of Uromune® from Red Leaf Medical) because of the huge unmet need for better preventative therapy for our Canadian women with recurrent UTI.

Responsibilities:

Principle Investigator ([name]) Responsibilities – will assume sponsor responsibilities: The PI ([name]) will be responsible for protocol development, diary and CRF development, IRB approvals, informed consent, inclusion/exclusion criteria confirmation, safety monitoring, data analysis, and presentation/publication of results..

Supplier (Red Leaf Medical) Responsibilities: Red Leaf Medical will be committed to providing Uromune® for 80 participants to be enrolled in the trial. The Supplier is not committed to provide funds to the investigator, [name] or provide any further financial support for the trial.

References:

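### The responder definition counts a woman who starts antibiotic prophylaxis after Day 1 and stays free of UTI as a vaccine success, which does not fit the stated aim

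*Combined protocol and SAP*

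**What the plan says.** **Aim.** The Rationale for Study Design wants to know whether Uromune is an acceptable "prophylactic option in lieu of continuous and/or interval antibiotic dosing for Canadian women" with recurrent UTI. Each woman's own UTI history is the control; there is no concurrent arm.

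**Primary outcome (Analysis).** "The individual participant will be considered a complete responder if they have no UTI requiring antibiotics reported in the 12 months since initiating therapy". Success is declared if "more than 50% of participants undergoing therapy has no reported UTI in the 12 months after initiation of therapy". The Study Synopsis also defines a responder by absence of UTI. None of these statements mentions antibiotics taken for prevention.

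**Secondary outcome (Analysis).** "The number of UTI in individual participants requiring antibiotics in the 12 months after starting therapy will be compared" with the number before therapy, taken as the previous 12 months' count or twice the previous 6 months' count. Prophylaxis in either period is not mentioned.

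**Prophylaxis.** The only rule is in the Exclusion Criteria: "Taking any prophylactic antibiotics at screening. Any prophylactic antibiotics must be stopped the day of the screening visit". Table 1 has eligibility reviewed again at Baseline. No rule applies after that.

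**Analysis sets.** Efficacy and safety use an "intent to treat analysis of all participants who took at least one dose of the Uromune". The per-protocol set is those who completed the 3-month regime.

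**Data.** Table 1 lists concomitant medications at every visit and phone call. No endpoint or analysis refers to them.

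**The concern.** Prophylaxis taken without a UTI is not a UTI requiring antibiotics, so it does not count against response. If a woman starts daily, post-coital or other interval antibiotics at Month 4, having had no on-study UTI, and reaches Month 12 without one, she is a complete responder. Yet for her the vaccine did not replace antibiotics, which is what the trial set out to learn. Following the plan exactly can therefore give a responder rate that does not answer the stated aim.

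The situation is plausible. The Background says some women with recurrent UTI are managed on long-term low-dose antibiotics. The study is described as real-life practice, and 9 of the 12 months of follow-up come after vaccine treatment has ended. Without a concurrent arm, no comparison group would show the effect of on-study prophylaxis. The study is also open label, so a scoring rule left until the end would be chosen with outcomes known.

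**Working it through.** **Step 1. Who is affected on the primary outcome.** There are three cases under the definition as written.

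| Course after Day 1 | Scored as | Does prophylaxis alter the score? |
|---|---|---|
| Prophylaxis before any on-study UTI requiring antibiotics, then no UTI | Responder | Yes, if she would otherwise have had a UTI |
| Prophylaxis before any such UTI, then a UTI requiring antibiotics | Non-responder | No |
| UTI requiring antibiotics first, then prophylaxis | Non-responder already | No |

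Only the first row can raise the responder rate. The intent-to-treat set keeps all three women, and the per-protocol set keeps all three if they finished the 3-month course.

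**Step 2. Size per woman.** Planned enrolment is 80. One woman is 1/80 = 1.25 points. This is an upper limit for the inflation, because some of these women would have stayed free of UTI without prophylaxis. Two to eight such women give at most 2/80 = 2.5 to 8/80 = 10 points.

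**Step 3. When it changes the conclusion.** More than 50% of 80 means at least 41 responders. If first-row women were scored as non-responders, success would be lost once the count fell to 40:

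| Responders as now defined | Rate | First-row women needed to lose success |
|---|---|---|
| 41 | 51.3% | 41 − 40 = 1 |
| 44 | 55.0% | 44 − 40 = 4 |
| 48 | 60.0% | 48 − 40 = 8 |
| 62 | 77.5% | 62 − 40 = 22 |

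The plan's planning rate is 59/75 = 78.7%, given there as 78%. At a true rate of 78%, the exact binomial probability of at least 41 of 80 is above 99.99%. The gap matters near 50% and hardly at all near 78%.

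**Step 4. Chance of declaring success, under assumptions.** The documents give no rate of starting prophylaxis. Let pv be the response rate without prophylaxis, q the share starting it, and pa the share of starters who remain responders. The scored rate is p = pv(1 − q) + pa·q, and success is at least 41 of 80. With pa from 60% to 90%:

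| pv | q | p | Chance of success |
|---|---|---|---|
| 40% | 0 | 40% | 2.7% |
| 40% | 10% | 42% to 45% | 6.0% to 15.6% |
| 40% | 20% | 44% to 50% | 11.7% to 45.6% |
| 45% | 0 | 45% | 15.6% |
| 45% | 20% | 48% to 54% | 31.9% to 72.8% |

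These are upper-end scenarios. A pa of 60% to 90% supposes that the starters begin close to Day 1, before any UTI. Women who start after a UTI have pa = 0.

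**Step 5. Secondary count.** Suppose 3 UTIs a year before entry, no vaccine effect, 3 a year off prophylaxis, 0.5 to 1.0 a year on it, and 20% of women on it for all 12 months (all assumed). The mean afterwards is 0.8 × 3 + 0.2 × 0.5 = 2.5, up to 0.8 × 3 + 0.2 × 1.0 = 2.6. That is an apparent fall of 0.4 to 0.5 UTIs per woman. Prophylaxis during the prior year works the other way: it lowers the comparator and so hides benefit. The two cannot be netted from the documents.

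**Step 6. Stopping the count at prophylaxis.** Take a woman with 4 UTIs in the prior year, 1 in Month 2, then prophylaxis and no more. The full 12-month count goes from 4 to 1, a fall of (4 − 1)/4 = 75%. Stopped at the end of Month 2, she has 1 × 12/2 = 6 a year against 4, a rise of (6 − 4)/4 = 50%. Neither figure is neutral.

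**The case against.** The instruction "Any prophylactic antibiotics must be stopped the day of the screening visit" may be meant to keep women off prophylaxis throughout. It is an eligibility criterion, though, with no on-study restriction and no consequence for scoring, so it does not supply the missing rule.

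A reader might infer that women doing badly on the vaccine are switched to antibiotics and then counted as successes. The documents do not support that for the primary outcome: a woman switched after a UTI requiring antibiotics is already a non-responder and cannot recover. The route left is narrow, its size is not given, and this objection stands.

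A reader might also infer that the whole bias favours the vaccine. For the secondary outcome that goes too far, because prior-year prophylaxis may have lowered the comparator.

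Counting outcomes whatever later care is given is a recognised choice, and it suits a real-life study analysed by intent to treat. The Objective, prevention of recurrent UTI, is compatible with it. But the aim in the Rationale is replacement of antibiotic dosing, and that favours counting prophylaxis as failure. The plan does not say that it has chosen the other strategy.

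Finally, the exposure should be visible: concomitant medications are reviewed at every contact, diaries record treatment received, and monitoring may check both concomitant medication and protocol deviations. This makes the gap easy to close, but it does not close it.

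**Conclusion.** The point holds within limits. The responder definition can credit the vaccine with a woman who went on to prophylactic antibiotics before any on-study UTI, and no other rule in the plan corrects this. The inflation is at most 1.25 points per such woman, assuming all 80 are enrolled and dosed. The number of such women is unknown. The result can turn on them only if the responder rate is near the success line of 41 of 80.

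For women switched after an on-study UTI, the effect is confined to the secondary count. On-study prophylaxis lowers the post-treatment figure there, but the net direction of the before-and-after comparison is uncertain.

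It would be too strong to conclude that the trial is likely to declare a false success. That needs both a rate near 50% and enough early starters, and the documents establish neither. In a single-centre, uncontrolled pilot this should be fixed before analysis, but it does not invalidate the design.

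**What to change.** 1. **Primary outcome.** In the Analysis section, and to match in the Study Synopsis, define a complete responder as a woman with no UTI requiring antibiotics and no start of continuous, post-coital or other interval antibiotic prophylaxis for UTI in the 12 months. Apply this in both analysis sets. Report the present UTI-only definition as a sensitivity analysis.
2. **Secondary outcome.** Keep the full 12-month count as planned. Report how many women started prophylaxis and when. Add a supportive sensitivity analysis, for example the count and follow-up time up to the start of prophylaxis. State that stopping there is informative, because prophylaxis tends to follow a UTI, and that it can bias against the vaccine.
3. **Data.** Confirm that the concomitant-medication case report form records start date and indication, so that prophylaxis can be told apart from treatment. The form is not among the documents, so this cannot be assumed.

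The change affects scoring only and does not restrict anyone's care. It adds no visits. The cost is a possibly slightly lower responder rate, a little more analysis work, and a form amendment if date or indication is not already captured.

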The proposal is for a real life clinical practice study in which female participants with a predefined history of recurrent UTIs in the previous year will be treated with 3 months of oral vaccine with a further 9 months of follow-up. The primary outcome will be no UTI in the 12 months following initiation of the vaccine (definition of a responder). A clinically significant and important outcome will be defined as a responder rate of 50% (50% of participants who had at least 3 UTIs in the previous year reporting no UTIs after therapy initiated.

Study Protocol

Study Participants

Main Inclusion Criteria:

Eligible participants will include women with at least 3 reported UTI episodes requiring antibiotics in the preceding 12 months or at least 2 reported UTI episodes requiring antibiotics in the preceding 6 months. In both cases, at least one of the episodes must be associated with a positive urine culture with a traditional and accepted uropathogen.

Other inclusion Criteria:

- Female participant \geq 18 and \leq 75 years of age at time of screening.
- Can provide written consent and willingness to comply with all aspects of study treatment and study requirements.
- Individuals who have had at least 3 episodes of a UTI in the past 12 months or 2 UTI episodes in the past 6 months. At least one of the UTI episodes must be associated with a positive urine culture with a traditional uropathogen including Escherichia coli, Proteus spp., Staphyloccous sp., Enterococcus sp., Klebsiella sp., or Pseudomonas aeruginosa.
- Post-menopausal for a minimum of 1 year or negative pregnancy test if participant is of child bearing potential and agreement to acceptable contraceptive use from Screening Visit 1 to final follow up visit if

participant is sexually active. Medically acceptable methods of contraception include hormonal contraception (i.e. estrogen, and/or progesterone or preparations that contain a combination of these hormones), non-hormonal intrauterine device or double barrier method (i.e. condom with foam or vaginal spermicidal suppository, or diaphragm with spermicide) or vasectomy of sole sexual partner. Complete abstinence alone can be used as a method of contraception.

• Free of a urinary tract infection at the time of trial inclusion.

Exclusion Criteria

- History of bladder tumours including uterine, cervical, vaginal or urethral cancer.
- Worrisome post-voiding residual (investigator's discretion).
- Infection related to urinary lithiasis.

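### Applied as written, the primary rule counts a woman who leaves early without a UTI as a 12-month responder; the plan has no observation requirement or censoring rule to prevent this

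*Combined protocol and SAP*

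**What the plan says.** The Analysis section, under Primary outcome, has a participant "considered a complete responder if they have no UTI requiring antibiotics reported in the 12 months since initiating therapy". The same paragraph gives the threshold twice. First: "A 50% responder rate of all enrolled participants will be considered a very clinically significant result". Then the pass/fail criterion: "more than 50% of participants undergoing therapy has no reported UTI in the 12 months after initiation of therapy". The Study Synopsis puts it differently: "The primary outcome will be no UTI in the 12 months following initiation of the vaccine (definition of a responder").

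The analysis set for efficacy and safety is an "intent to treat analysis of all participants who took at least one dose". For the second set, "A per protocol efficacy analysis will include all participants who completed the 3 month treatment regime". The Number of Participants paragraph plans 80 women "with an expected drop out rate of 15" per cent.

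The Participant Withdrawal and Early Termination sections ask for a termination visit, at which UTI history is taken. Neither says what outcome the leaver is then given.

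The secondary outcome compares UTIs after starting therapy with the history, defined as "number over previous 12 months or 2 X the number over the preceding 6 months".

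**The concern.** The responder definition turns on whether a UTI was reported, not on whether the woman was watched for 12 months. Because the analysis set keeps everyone who was dosed, a UTI-free leaver is credited with months nobody observed. The diary does not help: after month 3 it is filled in only when a symptom occurs, so silence from a leaver looks the same as freedom from UTI. The per-protocol set does not help either, because a woman who completes treatment and leaves at month 4 belongs to both sets.

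The error runs in one direction, in favour of the product. The study is an open-label pilot without a control arm, yet it has a stated pass/fail criterion, and the principal investigator is responsible for the data analysis. The classification of leavers should therefore be fixed before results are seen.

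The secondary outcome has a related, smaller problem. History is put on a 12-month scale, but leavers' post-therapy counts come from a shorter window and are not scaled.

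**Working it through.** **Inputs from the plan.** 80 participants; 15% dropout, so 0.15 × 80 = 12 leavers and 68 completers; success above 50%, so at least 41 of 80 (40/80 = 50.0% fails, 41/80 = 51.25% passes); anticipated rate 78% (59/75 = 78.7%). The plan gives no alpha, test or power for its convenience sample, so there is no stated calculation to reproduce.

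**Assumptions.** All 12 leavers were dosed; they leave evenly over the 12 months; the UTI hazard is constant and unrelated to leaving.

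**Rate under the literal rule.** Let p be the true 12-month UTI-free proportion and h = −ln(p). The chance that a leaver leaves UTI-free is q = (1 − p)/h. The literal rate is (68p + 12q)/80, so the overstatement is 0.15(q − p).

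| True p | q | Literal rate | Overstatement |
|---|---|---|---|
| 45% | 0.689 | (30.6 + 8.27)/80 = 48.6% | 3.6 points |
| 55% | 0.753 | (37.4 + 9.03)/80 = 58.0% | 3.0 points |
| 78% | 0.885 | (53.04 + 10.62)/80 = 79.6% | 1.6 points |

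**Chance of meeting the criterion.** Literal rule: P(Bin(68, p) + Bin(12, q) ≥ 41). Complete follow-up: P(Bin(80, p) ≥ 41). Kaplan-Meier: 20,000 simulated trials of 80 with 12 evenly spread leavers; mean estimates were 45.0% and 55.0%, so it is unbiased under these assumptions.

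| True p | Literal | Kaplan-Meier | Complete follow-up |
|---|---|---|---|
| 45% | 35.5% | about 19% | 15.6% |
| 55% | 91% | about 80% | 78% |

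**How often the verdict differs, literal against Kaplan-Meier.** About 15-16% of simulated trials at a true 45%, 19% at 50%, 11% at 55%, 3% at 60% and 0% at 78%. The literal rule is the one that passes in each of these.

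**Sensitivity of the literal rule at a true 45%.** With 8 leavers: 47.4%, chance of passing 28%. With 16: 49.8%, 44%. With all 12 leaving within 6 months: 50.6%, 50%.

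**Outer bounds at 78%.** UTI-free leavers as non-responders: 0.85 × 0.78 = 66.3%. Literal rule: 79.6%.

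**Secondary outcome.** If the 15% who leave lose 3 to 9 months, the mean post-therapy count is too low by about 0.15 × 3/12 = 3.75% to 0.15 × 9/12 = 11.25%.

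**The case against.** A reader might infer that the plan has deliberately chosen to count leavers as responders. It has not. The Study Synopsis wording, which it labels the definition of a responder, omits the word reported and can be read as needing 12 UTI-free months. The plan also models itself on 75 evaluable women from the UK report, which could suggest analysing completers only. On that reading 35 of 68 are needed, and the chance of passing at a true 45% is 17.1%, close to complete follow-up. That reading conflicts with the at-least-one-dose set. What stands is that the intention is open; what remains is that the operative definition, applied to the stated set, gives the literal result.

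A reader might also set the literal rule against counting every UTI-free leaver as a failure. Those two give opposite verdicts in 35% of trials at a true 45% and 69% at 55%. That contrasts two extremes, neither of which is a sensible primary analysis. The fair comparison is with Kaplan-Meier, where disagreement peaks near 19%.

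The count of 12 dosed leavers is an assumption. The plan does not define dropout and provides for withdrawal between screening and baseline; women lost there take no dose and fall outside the analysis set, so the effect shrinks.

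Finally, the event is worded with and without the antibiotic requirement. The shorter form may be shorthand, and the documents give no basis for a figure. It is worth tidying, but it is not evidence of bias.

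**Conclusion.** The point holds as a should-fix. The rule as written credits unobserved UTI-free months to early leavers, and no statement elsewhere corrects it. Under the stated assumptions the overstatement is about 3 points at true rates of 45-55%, and at a true 45% the chance of declaring success is roughly 1.8 times that under Kaplan-Meier (35.5/19). It grows if dropout is heavier or earlier, and shrinks if some of the 15% leave before dosing.

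The documents do not support inferring that the trial's conclusion is at risk if the vaccine performs as anticipated: at 78% the criterion is met under every classification, and only the reported rate moves.

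**What to change.** 1. In the Study Synopsis and the Analysis section, use one event (UTI requiring antibiotics), one set (at least one dose) and one threshold (more than 50%).
2. State that a woman without a UTI who is not observed for 12 months is not a responder by default. A UTI before leaving is a failure; otherwise she is censored at the last contact where UTI history was taken. A woman whose UTI history covers the full 12 months is a completer even if her final visit falls outside the ±7-day window.
3. Make the Kaplan-Meier 12-month UTI-free proportion, with 95% CI, the primary estimate, and keep the point-estimate criterion of more than 50%. Report UTI-free leavers as non-responders and as responders as sensitivity bounds. Take UTI dates from the diary or medical records; where a date is missing, place the UTI in the interval between the contacts on either side of it.
4. For the secondary outcome, compare UTIs per person-year before and after, with log follow-up time as offset and allowance for within-participant correlation.

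**Cost.** Wording and standard programming. UTI history is already scheduled at every follow-up contact and at Early Termination, and the post-treatment diary asks for symptom dates, although leavers may not return it. Kaplan-Meier assumes dropout is unrelated to UTI risk; the two bounds show how much that could matter. Its 95% CI is about ±11 points near 50% (1.96 × 0.058), so a pass just above the threshold is weak evidence. The reported rate will be slightly lower than under the literal rule.

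### The primary endpoint is declared achieved on an observed responder rate above 50%, with no allowance for sampling error and no error-controlled test behind the claim of adequate power

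*Combined protocol and SAP*

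**What the plan says.** The Analysis section, under Primary outcome, defines a "complete responder if they have no UTI requiring antibiotics reported in the 12 months since initiating therapy". It then sets the success criterion: the endpoint is "achieved if a clinically significant and important level of more than 50% of participants undergoing therapy" meet that standard.

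The 50% figure is described as a clinical benchmark. The same paragraph states: "A 50% responder rate of all enrolled participants will be considered a very clinically significant result". The Study Synopsis says "A clinically significant and important outcome will be defined as a responder rate of 50" per cent, without the words *more than*.

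The sample is "80 participants in total (with an expected drop out rate of 15" per cent). Rationale for Study Design explains that it is a "convenience sample based on the number of individual Uromune® doses to be provided by supporting company". On adequacy, the Primary outcome paragraph cites the UK early-experience result of 78% and says "our convenience sample should be sufficient to power our analysis".

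The analysis set is an "intent to treat analysis of all participants who took at least one dose of the Uromune". The document gives no null hypothesis, significance level, test or confidence interval for the primary endpoint, and does not say how participants who drop out are classified.

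**The concern.** The rule turns an observed percentage into a yes/no conclusion and ignores how far that percentage could lie from the true rate by chance. In a single-arm study with no concurrent control, this threshold is the whole of the primary efficacy decision. A result one participant over the line would be reported as an endpoint achieved, although the data would be compatible with a true rate around 40%.

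The power statement adds to the difficulty. Power belongs to a decision rule with a stated error rate, and here there is none. A reader would take the sentence to mean that a formal calculation supports the conclusion.

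**Working it through.** **The plan's own figure.** There is no stated power or error rate to reproduce, because N = 80 was set by product supply. The benchmark proportion is 59/75 = 78.7%, given in the protocol as 78%.

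**Inputs.** From the documents: N = 80; 15% dropout, so 80 × 0.85 = 68 completers; success if the observed rate exceeds 50%; expected rate 78%. My assumptions: independent participants (binomial counts), and, for the alternative rule only, a two-sided 95% confidence level.

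**Step 1: the rule as written.** More than 50% of 80 means X ≥ 41; more than 50% of 68 means X ≥ 35. The chance of declaring success is P(X ≥ r | n, p), the exact binomial upper tail.

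| True rate p | n = 80, r = 41 | n = 68, r = 35 |
|---|---|---|
| 40% | 2.7% | 3.6% |
| 45% | 15.6% | 17.1% |
| 50% | 45.6% | 45.2% |
| 60% | 95.6% | not computed |
| 78% | >99.9% | >99.9% |

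If the Synopsis wording is read as at least 50%, then r = 40 and the probability at a true 50% is 54.4% for n = 80.

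These rates apply to everyone analysed. If 50% held only among completers and the 15% who drop out counted as non-responders, the overall rate would be 0.50 × 0.85 = 42.5%, and P(X ≥ 41 | 80, 0.425) = 7.1%.

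**Step 2: the smallest success.** 41/80 = 51.3%, with an exact (Clopper-Pearson) 95% CI of 39.8% to 62.6%. The half-width is (62.6 − 39.8)/2 = 11.4 points. The normal approximation gives 1.96 × √(0.5 × 0.5/80) = 11.0 points.

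**Step 3: requiring the lower 95% limit to exceed 50%.** 49/80 has a lower limit of 49.7%, which fails; 50/80 has 51.0%, which passes. The threshold is therefore 50/80 = 62.5%. At a true 50%, P(X ≥ 50 | 80, 0.50) = 1.6%.

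| Assumption | Overall true rate | P(X ≥ 50), n = 80 |
|---|---|---|
| 78% applies to all analysed | 78% | 99.9% |
| 78% in completers, 15% dropouts count as non-responders | 0.78 × 0.85 = 66.3% | 80.0% |
| True rate 60% | 60% | 36.9% |

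At 66.3% the written rule (X ≥ 41) succeeds 99.8% of the time; at 60%, 95.6%.

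**The case against.** The strongest counter-argument is that 50% is not a null value in this protocol. The text calls a 50% rate very clinically significant, so a trial that succeeds about half the time at a true 50% is not making an error by its own definition. A reader might infer that the 45.6% is a false-positive rate; the documents do not support that. The relevant figures are those below the target: 15.6% at a true 45% and 2.7% at 40%. The rule also separates 40% from 60% well. This objection stands.

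A reader might also infer that a lower-limit rule costs nothing because power at 78% is 99.9%. That holds only if 78% applies to everyone analysed. The protocol says the 78% came from women who completed treatment, while the planned analysis includes all who took one dose and 15% are expected to drop out. With dropouts counted as non-responders, power is 80.0%. At a true 60%, above the protocol's own benchmark, the stricter rule fails about 63% of the time. This objection stands as well, and so does the point that a two-sided 95% level is a choice: a one-sided 5% test would need 48/80.

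Finally, this is a single-centre, open-label pilot for a preliminary assessment. The only stopping rule concerns safety, and no licensing or go/no-go step is tied to the endpoint. That lowers the severity, but it does not justify calling an endpoint achieved without an interval, or claiming power with no test to power.

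**Conclusion.** The concern holds in a limited form. The plan declares the primary endpoint achieved on a point estimate and asserts power without an error-controlled test. With 80 analysed, the declaration would be made 15.6% of the time at a true 45%, below the protocol's benchmark, and 45.6% of the time at exactly 50%. The smallest qualifying result leaves true rates from 39.8% to 62.6% compatible with the data.

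These figures assume binomial counts and a true rate that applies to all 80; at 68 analysed they barely change. They would change with the dropout rule, which the documents leave open.

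The documents do not support describing this as a 46% type I error, or presenting 50/80 with 99.9% power as the one correct replacement. Given the pilot purpose, it should be corrected but is not critical.

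**What to change.** In the Primary outcome paragraph:

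1. Report the responder rate with its exact (Clopper-Pearson) 95% CI in the population that took at least one dose. Use that denominator and a single wording of the benchmark throughout: the text now varies between all enrolled, those undergoing therapy and those dosed, and between 50% and more than 50%.
2. Keep 50% as a clinical benchmark. Either drop the word achieved, or use it only when the lower confidence limit exceeds 50%.
3. Replace the power sentence with the precision at n = 80: about ±11 percentage points near 50%.
4. State how participants who drop out before 12 months are classified.
5. If the lower-limit rule is chosen, give its threshold (50/80), its one-sided error at a true 50% (1.6%), and its power under the stated dropout rule: 99.9% if 78% applies to all analysed, 80.0% if the 15% dropouts count as non-responders.

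The cost is one paragraph of wording, with no added participants, visits or product. Reporting the interval has no statistical downside. The lower-limit rule does: the observed rate needed rises from 51% to 62.5%, and at a true 60% it succeeds only about 37% of the time. For a pilot, estimation against the benchmark, without a declaration of success, is the simpler choice.
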